We will conduct a mixed-methods study (concurrent QUANT-qual), using a CBPR approach, in preparation for a future cluster randomized hybrid effectiveness/implementation trial. Qualitative data will supplement quantitative data to obtain a deeper understanding of implementation issues and patient and provider experiences, to further explore potential mechanisms of action, and to help interpret quantitative findings. We will start by working with representatives from each intervention site to determine how to integrate the toolkit into their practices and track implementation efforts. We will pay attention to what might be done similarly across systems and what has to differ to accommodate practice needs. We will then conduct a 6-month, non-randomized, controlled, pilot study in 5 intervention sites and 5 control sites. Though control sites are sometimes considered an unnecessary use of resources in pilot-studies, in this case, it is important to collect data from control sites to 1) ensure that we can obtain adequate recruitment and retention rates, even without offering an intervention, 2) to assess for potential contamination being that patients and providers are free to use the publicly available toolkit, and 3) to obtain more robust efficacy data on the toolkit's short-term outcomes and potential mechanisms of action than we could in our prior 1-month, single-arm trial.

Figure 2: Change Model

Our study is based on the conceptual model we developed from our qualitative work (see Preliminary Results). This model views successful healthcare outcomes as being dependent on the interaction between patient- and provider-level factors within a larger context of system-level factors. We developed the toolkit to target potential leverage points within this model. Specifically, it is meant to give patients and providers the tools they need to improve their self-efficacy while encouraging providers and staff to use desired, patient-specific accommodations and recommended strategies. We hypothesize that doing so will improve patient-provider

communication and decrease barriers to healthcare, with possible long-term impacts on unmet healthcare needs and healthcare utilization. **Figure 2** shows our proposed change model.

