Qualitative interviews with patients, providers, and staff	Better understanding of toolkit impact	Semi-structured questions reflecting on experience with toolkit	Mechanisms of action	3	
	Better understanding of implementation process	Semi-structured questions around the implementation	Implementation strategy refinement	1, 4	
Administrative data	Healthcare utilization	Primary care, ED, and preventive care	Long-term outcome	4	

Toolkit integration and process evaluation:

During the start-up phase, we will meet with providers, administrators, and staff from each intervention clinic to create a plan for how best to integrate the toolkit into clinical practice. For example, the clinic may choose to set up a protocol for scanning AHAT reports into the EMR, flagging patient charts to alert providers to the existence of the AHAT, communicating relevant recommendations to front office and back office staff, setting up follow-up appointments, if needed, creating EMR templates to help providers document discussions or changes, and responding to challenges implementing requested accommodations.

We will then conduct a process evaluation spanning the duration of the project. Using Stetler's classification system, ⁴⁵ this assessment would be considered a formative implementation-focused evaluation. The purpose is to resolve actionable barriers, enhance identified levers of change, and refine future implementation efforts by analyzing discrepancies between the implementation plan and its operationalization. As part of this evaluation, we will measure a variety of quantitative process measures including: 1) recruitment and retention rates; 2) completion of AHAT reports; 3) use of other portions of the toolkit site; and 4) proportion of AHAT reports scanned into the EMR. We will collaboratively determine how to feasibly collect additional process information to track fidelity with the implementation protocols the clinics developed. We will use qualitative data to more fully understand the implementation experience (see below). Such data will focus on patient, provider, staff, and administrator perceptions of the Toolkit's utility, how the toolkit was used, barriers and facilitators to successful uptake and integration, and recommendations for change to the implementation plan.

Survey and Administrative Data Collection:

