Patient Survey: All patient participants will be asked to take surveys at baseline and at six months. After logging into their secure account, participants complete surveys online (independently or with help from a supporter) using our Audio Computer Assisted Survey Instrument (ACASI), a highly accessible system with a read-aloud option and other features designed to meet the needs of people with disabilities. ⁴⁶ Participants without Internet access can take the survey at their primary care clinic or the PSU or Kaiser research offices.

After completing the baseline survey, participants from intervention sites will be automatically directed to use the AHAT to create a personalized report. After reviewing the report, they will be asked permission to have the report sent directly to their PCP. Participants will then be directed to the remainder of the toolkit (on a password-protected research site), where they can read information about health and healthcare and download worksheets and checklists. The research version of the toolkit will be accessible through participants' personal accounts to better track participants' use of components of the toolkit. Clinics will be expected to use the implementation protocol they developed to ensure the AHAT report reaches appropriate staff and that recommended strategies and accommodations are incorporated into the patient's care. Six months later, all participants will be re-contacted and asked to participate in the follow-up assessment. To increase retention, we will collect various types of contact information and will request permission to use updated information from clinical records, if needed. Participants will receive \$30 for completing both surveys.

We will collect data on patient provider communication using items we previously adapted⁶ from 2007 Health Information National Trends Survey (HINTS).⁴⁷⁻⁵⁰ We clarified wording and added two new items on expressive and receptive comprehension as community partners felt this was not adequately addressed in the initial scale. The scale asks patients about their last visit with their PCP. Responses use a 4-point Likert scale with anchors of "Never" to "Always". The scale is scored by summing the responses. In the post-test, participants will only be asked this scale if they have seen their PCP during the 6-month study. The original HINTS patient-provider communication scale and our adapted version both had a Cronbach's alpha of >=0.9.^{6,51}

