to do a confirmatory factor analysis and re-test its psychometric properties in preparation for the larger RCT. We will also create and test a new measure on satisfaction with provider/staff use of desired accommodations.

We will assess unmet healthcare needs and healthcare utilization, using items we previously adapted⁶ from the 2002/2003 Joint US Canada Survey^{54,55} and the 2007 National Health Interview Survey (NHIS) Questionnaire - Adult Access to Health Care & Utilization.^{56,57} We will measure unmet healthcare needs using the item "During the past 6 months, there was a time when I felt that I needed the following type of healthcare, but did not receive it. (Check all that apply)." Response options include six types of healthcare (e.g., "medical care for a physical health problem," "mental healthcare or counseling"). As in the past, we will ask a variety of questions about outpatient, ED, and hospital visits and use of preventive services, however we will also obtain EMR and claims data from each health system about participant use of these services and compare results.

In the baseline survey, we will collect data on demographic and disability-related characteristics. In the 6-month follow-up participants in the intervention arm will answer a set of close- and open-ended evaluation questions about their satisfaction with the toolkit, which parts they found most useful, why they did not give permission to share their AHAT report, whether they discussed the report with the PCP, and what changes, if any, they felt occurred in response to the toolkit. To assess for contamination, the 6-month follow-up survey will include an item asking participants if they have used the public version of the toolkit. Patients in the control clinics will be given a link to the public site at the end of the study.

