Provider Surveys: We are acutely aware of the importance of minimizing the burden of this study on PCPs, both in the current study and in the future R01. As such, we will use patient surveys and administrative data to answer most of our research questions, and will only conduct in-depth interviews with 3 providers from each intervention site (N=15). However, we believe that provider self-efficacy may be an important mechanism of action that needs to be assessed directly from all providers. We will conduct an extremely brief survey (<5 minutes) at baseline and at the end of the study with all providers who have autistic patients in their panels (N 50-80). Providers may participate via email, fax, telephone, or online. The survey will include items on self-efficacy and attitudes toward autistic adults. Follow-up surveys will also include an item about whether they are aware of the AASPIRE Healthcare Toolkit and, if so, a few items about their satisfaction with the toolkit.

Administrative Data: We will use administrative data from each health system to assess healthcare utilization. Obtaining such information is relatively straightforward for a closed healthcare system such as Kaiser. However, it is more complex in non-integrated systems. We will explore how well we can capture data from the OHSU and Legacy Systems using EMR data, including Care Everywhere (an Epic System that links EMR visits from most local health systems) and claims data from Health Share (the Medicaid managed care coordinated care plan for our county). Though this study will not be powered to show a difference in unmet needs or healthcare utilization, these data can help inform the future R01. It will also give us experience working with this type of administrative data from each health system.

Quantitative Data Analysis

Our quantitative analysis plan includes descriptive and psychometric analyses, assessment of missing data and attrition, and a mixed effects regression analysis to compare results from intervention and control sites while adjusting for demographic and disability-related characteristics. We will conduct analyses using STATA 14 (Statacorp, College Station, Texas). We will use an intention-to-treat approach for all analyses.

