Preliminary analyses will include careful examination of descriptive statistics and distribution for each of the study variables at baseline and the 6-month follow-up. This will include stratified analyses within the intervention and control groups. For variables measured with multiple items, psychometric analyses (Cronbach's alpha, confirmatory factor analysis) will be conducted to instigate internal reliability, and, when necessary, measurement modifications will be made to improve reliability.

We will use two independent sample T-tests to test bivariate differences between the main independent variable (intervention vs control clinic) and baseline continuous variable subject characteristics and Chisquare/Fisher-Exact test to assess differences between the main independent variable and categorical variables. We will apply similar tests to primary outcomes and secondary outcomes at each time point.

We will test Aim 2 hypotheses using multivariate regression models. The dependent variable in each of our primary analyses will be the 6-month change in short-term outcomes (patient-provider communication score and number of barriers). We will calculate change by subtracting the baseline score from the score at 6 months. We will also conduct exploratory analyses using the 6-month change in scores for the potential

mechanisms of action (e.g., self-efficacy, use of accommodations) and long-term outcomes (e.g., unmet needs, emergency department use) as the dependent variable. Analyses will use linear vs logistic models depending on whether the outcome is continuous (e.g., patient-provider communication score) or binary (e.g., ED use, unmet needs). The predictor will be study arm (intervention vs control). We will adjust for potential confounders including data source (direct report vs proxy), age, gender, race/ethnicity, residence (own home vs with family of origin); need for support to communicate with providers; health status, and unmet needs at baseline.

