Power Considerations: We plan to enroll 250 participants to have complete follow-up data on at least 200 (100 intervention;100 control), which will allow us to detect an effect size of 0.4 with a power of 80% using an independent sample t-test test with a two-tailed hypothesis and an alpha of 0.05. It would provide 97% power to detect an effect size of 0.5. Though one must use caution in deriving effect sizes from small pilots, based on our preliminary results, we feel it is reasonable to expect this level of change in our short-term outcomes. For example, we noted a 0.55 effect size in the number of barriers to healthcare. We are using a conservative estimation to compensate for the complex multivariate analyses proposed in Aims 2 and 3.

Qualitative Interviews with Patients, Providers, Staff, and Administrators

Participants and Sampling: We will collect qualitative data from 30 patients, 15 providers, and 15 administrators/staff selected from the 5 intervention sites to better understand the implementation process and the tool's potential impact. We will use maximum variation sampling,⁵⁸ a purposive sampling strategy which increases depth of understanding by selecting a diverse group of individuals who are expected to have different perspectives. We will use data from our quantitative surveys to identify which patient and supporter participants to invite to the qualitative study. The goal will be to create a patient sample that has wide distribution of the following characteristics: 1) gender; 2) age, 3) race/ethnicity, 4) living situation, 5) need for assistance to receive healthcare, 6) use of alternative and augmentative communication (AAC), 7) permission (yes/no) to share AHAT report with provider, and 8) clinic site. We will primarily recruit participants who have seen their PCP after using the Toolkit, as they are the ones most likely to provide rich, interesting information. However, we will intentionally sample 5 participants who did not see their PCP to try to understand potential barriers to care that were not addressed by the toolkit. We will recruit patient participants for an interview between 4-8 months after they complete the baseline survey. We will use a similar strategy to obtain a varied sample of providers and administrators/staff from each of the clinics, purposely sampling people who serve in a variety of roles in each clinic. Participants will receive an additional \$50 stipend for participating in an interview.

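### The primary communication outcome is scored at 6 months only in participants who saw their PCP, so its analysis compares visitors by assigned arm and is not intention-to-treat as the plan states for all analyses

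*Combined protocol and SAP*

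**What the plan says.** The Quantitative Data Analysis section makes the "6-month change in short-term outcomes (patient-provider communication score and number of barriers") the dependent variable of the primary analyses, calculated as the 6-month score minus the baseline score. The same section states: "We will use an intention-to-treat approach for all analyses".

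The Patient Survey section explains of the communication measure that "The scale asks patients about their last visit with their PCP", and then sets the follow-up rule: "In the post-test, participants will only be asked this scale if they have seen their PCP during the 6-month study". The barriers checklist carries no such condition.

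On sample size, Power Considerations says: "We plan to enroll 250 participants to have complete follow-up data on at least 200", split 100 and 100, for 80% power at an effect size of 0.4. The participant characteristics section repeats the 250 and the 200. Neither place says whether a participant without a communication score counts as complete.

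**The concern.** A participant with no PCP visit during the study has no 6-month communication score and therefore no change score. No section says how such a participant enters the communication analysis. The plan does promise an assessment of missing data and attrition, but it is not tied to this gap, which arises by design among people who were retained.

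What remains is a comparison of visitors by arm. Visiting occurs after allocation, and the plan treats it as something that may change. Table 1 lists primary care use among its long-term outcomes, the change model ends "with possible long-term impacts on unmet healthcare needs and healthcare utilization", and intervention clinics may adopt protocols that include "setting up follow-up appointments, if needed". If the toolkit changes who visits, the visitors in the two arms differ for a further reason, on top of the lack of randomisation. Followed as written, the plan would report this contrast as intention-to-treat. The pilot is also meant to refine outcome measures and power estimates for the larger trial, so an unlabelled visitor-only result would be carried into that design.

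**Working it through.** **Analysis population, by setting the sections side by side**

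1. Change is the 6-month score minus baseline, so no 6-month score means no change score.
2. The 6-month communication scale is given only to participants with a PCP visit during the study.
3. The communication analysis can therefore include only visitors, grouped by assigned arm.
4. Intention-to-treat is claimed for all analyses. Steps 1 to 3 keep the assigned arm but not the full set of participants, so the claim cannot hold for this outcome. It can apply to barriers, which is asked of everyone followed up.
5. The plan expects some non-visitors: the qualitative sampling section reserves 5 interviews for participants who did not see their PCP.

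**Power**

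Inputs from Power Considerations: 250 enrolled, 200 complete (100 per arm), effect size d = 0.4, two-sided alpha 0.05, independent-samples t-test. The share of completers with a PCP visit in 6 months is not in the documents. The shares below are assumptions and are taken as equal in both arms.

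Formula: power is the probability that a noncentral t variable with 2n − 2 degrees of freedom and noncentrality d × √(n/2) exceeds the two-sided 5% critical value.

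*The plan's figure.* With n = 100, the noncentrality is 0.4 × √50 = 2.83, and power is 80.4%. The stated 80% reproduces. With n = 99, it is 80.0%.

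*If complete data require a communication score.* The 80% stands. At 250 enrolled, retention × visit share must reach 200/250 = 0.80, so the minimum retention is 0.80 divided by the visit share:

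| Assumed visit share | Minimum retention |
|---|---|
| 95% | 0.80/0.95 = 84% |
| 90% | 0.80/0.90 = 89% |
| 85% | 0.80/0.85 = 94% |

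*If complete data do not require a communication score.* The communication analysis has 100 × visit share per arm:

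| Assumed visit share | n per arm | Noncentrality | Power at 0.4 | Effect detectable at 80% power |
|---|---|---|---|---|
| 100% | 100 | 2.83 | 80.4% | 0.40 |
| 90% | 90 | 2.68 | 76.1% | 0.42 |
| 75% | 75 | 2.45 | 68.2% | 0.46 |
| 60% | 60 | 2.19 | 58.4% | 0.52 |

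These figures keep the plan's own t-test basis and make no allowance for clustering by clinic.

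**The case against.** The strongest reply is that this is a matter of labelling. The plan says openly who is scored, a participant without a visit has nothing to rate, and the pilot reported the outcome the same way. That stands as a defence of the measurement rule, and nothing here asks for the scale to be given to non-visitors. It does not rescue the intention-to-treat statement, which covers all analyses without exception.

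Second, the evidence that the toolkit changes visiting is thin. The change model speaks of possible, long-term effects, and follow-up appointments are one example of what a clinic may choose. This also stands. A reader might infer that the communication contrast is shown to be biased; the documents do not support that, because they neither assert differential visiting within 6 months nor allow its effect to be sized or signed.

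Third, the plan already adjusts for baseline health status, unmet needs and need for support in communicating with providers, and already plans exploratory by-arm models of long-term outcomes. The adjustment may reduce selection into visiting but cannot be relied on to remove it. The exploratory models cover much of what is needed; what is missing is a visit yes/no row and its link to this outcome.

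Fourth, a reader might infer that the 80% power figure is wrong for communication. It is not shown to be: it holds if complete data include a communication score, which is a natural reading. The enrolment and completion targets are also minimums, and clinics can be added if recruitment falls short, so the retention thresholds above apply only if enrolment stops at 250. Nor can the earlier study's 43 visitors among 170 participants over one month be used as a 6-month visit rate.

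**Conclusion.** The concern holds as a mismatch between the stated analysis population and what the communication outcome allows. The plan claims a property that one of its two primary analyses cannot have, because that analysis conditions on a post-allocation event which the plan also studies as an outcome. Barriers is unaffected by the visit condition.

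This conclusion rests on the text alone and needs no assumed visit share. The consequence for power is conditional: none if complete data require a communication score, or a fall to about 76%, 68% or 58% at assumed visit shares of 90%, 75% or 60% if they do not. The correction should be made before analysis, since it changes what may be concluded from the communication result.

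**What to change.** 1. Describe the communication analysis as being among participants with a PCP visit during follow-up, by assigned arm. Limit the intention-to-treat statement to outcomes asked of all participants, such as barriers. Keep both outcomes primary.
2. Report the proportion with a PCP visit (yes/no) by arm, with baseline characteristics of visitors by arm, and interpret the communication contrast in that light. The data are already planned: the Patient Survey section says "we will ask a variety of questions about outpatient, ED, and hospital visits and use of preventive services", and EMR and claims data are to be obtained as well.
3. State whether the 200 with complete follow-up data must have a communication score. If they must, say that at 250 enrolled the 20% loss allowance covers dropout and non-visits together. If not, restate power for communication at the expected number with a visit, and give the assumed visit share.

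The cost is wording, one or two table rows, and possibly a less favourable power figure for one outcome. Data collection does not change.

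### Unmet needs and ED use are set up as 6-month change but given logistic models, which cannot be fitted as written; the two primary change analyses lack a baseline-adjusted sensitivity model

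*Combined protocol and SAP*

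**What the plan says.** All of this is in the combined protocol and SAP, mostly under Quantitative Data Analysis.

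- **Primary outcomes (communication score, number of barriers).** "The dependent variable in each of our primary analyses will be the 6-month change in short-term outcomes". The definition follows: "We will calculate change by subtracting the baseline score from the score at 6 months".
- **Exploratory outcomes.** The next sentence uses the 6-month change for the possible mechanisms of action and for "long-term outcomes (e.g., unmet needs, emergency department use) as the dependent variable".
- **Model type.** The plan then assigns "linear vs logistic models depending on whether the outcome is continuous (e.g., patient-provider communication score) or binary (e.g., ED use, unmet needs").
- **Covariates.** "We will adjust for potential confounders including data source (direct report vs proxy"), then age, gender, race/ethnicity and residence, and finally "need for support to communicate with providers; health status, and unmet needs at baseline". Baseline unmet needs is the only baseline value of an outcome on the list. Baseline communication, baseline barriers and baseline ED use are not named.
- **Other outcome comparisons.** The section opens by announcing "a mixed effects regression analysis to compare results from intervention and control sites". For the unadjusted two-sample tests it adds: "We will apply similar tests to primary outcomes and secondary outcomes at each time point".

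The Administrative Data paragraph says that the study is not powered for unmet needs or utilisation. Aim 4 nevertheless uses the study to help choose utilisation outcomes for the later trial.

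**The concern.** **Binary outcomes.** The text combines a dependent variable with three possible values and a model that takes two. An analyst has to recode, and no rule is given. The obvious repair is status at 6 months, but then subtraction no longer brings the baseline value in. Baseline unmet needs would still be in the model as a named covariate. Baseline ED use would not. Clinics are not randomised, so arms that already differed in ED use could differ at 6 months with no toolkit effect.

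**Primary outcomes.** The named covariates leave out each outcome's own baseline score. Raw change and a baseline-adjusted model rest on different assumptions when groups are not randomised, and they can give different answers if the arms start apart. The plan fits only the first. Leaving the baseline score out also usually costs some precision. What is at stake is how clearly the pilot's effect estimate can be read when the larger trial is planned.

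**Working it through.** **1. Binary outcomes.** With 0 = no and 1 = yes:

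| Baseline | 6 months | Change |
|---|---|---|
| 0 | 0 | 0 |
| 0 | 1 | +1 |
| 1 | 0 | -1 |
| 1 | 1 | 0 |

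A binary logistic model needs two categories. Improvement versus the rest, worsening versus the rest, and 6-month status are three different outcomes from the same data. The exploratory sentence could be read so that change covers only the mechanisms. The long-term outcome would then be binary, but its time point would still be unstated.

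**2. The plan's own power figure.** Power Considerations gives 100 per arm, effect size 0.4, two-sided alpha 0.05 and an independent-samples t-test. Recomputed power is 80.4% against the stated 80%, so it reproduces.

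**3. Precision formulas.** Let r be the correlation between baseline and follow-up. Assume equal SDs at both times, no clustering and no other covariates.

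- Variance of change = 2(1-r) SD²
- Residual variance after baseline adjustment = (1-r²) SD²
- Ratio, adjusted to change = (1-r²) / [2(1-r)] = (1+r)/2

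**4. r for communication.** The pilot (Evaluation of the Healthcare Toolkit) reports 43 people, p = 0.03 and effect size 0.26 at one month. Assume a paired t-test.

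- p = 0.03 on 42 df gives t = 2.25.
- SD of change / SD of score = 0.26 × √43 / 2.25 = 0.759.
- r = 1 - 0.759²/2 = 0.71.
- Units check: if 0.26 were in SD of change, t would be 0.26 × √43 = 1.70 and p about 0.10, not 0.03. SD of the score is therefore the likelier unit.
- Rounding of the reported figures alone gives 0.68-0.74. Sampling error is larger. Treating 0.71 as an observed correlation, Fisher z = 0.887 with standard error 1/√40 = 0.158, so the 95% limits are 0.577 and 1.197, or r of about 0.52 to 0.83.

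**5. Gain for communication**, with 0.4 in SD of change, 100 per arm and d = 0.4/√((1+r)/2):

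| r | Variance ratio | CI narrower by | d | Power |
|---|---|---|---|---|
| 0.52 | 0.760 | 13% | 0.459 | 89.8% |
| 0.71 | 0.855 | 8% | 0.433 | 86.1% |
| 0.83 | 0.915 | 4% | 0.418 | 83.7% |

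If 0.4 is in SD of the score, then at r = 0.71 change has d = 0.4/√(2 × 0.29) = 0.525 and power 95.9%. The adjusted model has d = 0.4/√(1-0.71²) = 0.568 and power 97.9%.

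Under Patient Survey, the follow-up communication scale is asked only of people who saw their PCP, so 100 per arm is optimistic for that outcome. With an assumed 50 or 80 per arm, r = 0.7 and SD-of-change units, power goes from 50.8% to 57.5%, or from 71.0% to 77.9%.

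**6. Barriers.** The pilot gives only p < 0.0001, which is a bound, so r cannot be recovered. For an assumed r of 0.3, 0.5 or 0.7, 80.4% becomes 93.7%, 90.1% or 86.3% in SD-of-change units.

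**7. Disagreement between the two models.** Let D0 and D6 be the arm differences at baseline and 6 months. Change estimates D6 - D0. The adjusted model estimates D6 - b·D0, and b = r with equal SDs. They differ by (1-r)·D0, which in SD of change is gap × √((1-r)/2), with the gap in SD of the score. The documents give no baseline gap. For an assumed gap of 0.1 or 0.3 SD at r = 0.71, the difference is 0.04 or 0.11 SD of change, against a target effect of 0.4.

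**The case against.** The strongest reply is that the primary-outcome part identifies no error, and that is right. Raw change is a defensible difference-in-differences estimate in a non-randomised study. A reader might infer that the primary analysis is invalid or that baseline adjustment must replace it; the documents do not support that. Nor can it be said that the plan has failed to choose, because it names change as primary.

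A reader might also infer that model dependence would stay hidden. That is too strong. The planned comparisons give D0 and D6 and the change analysis gives D6 - D0. For any slope b between 0 and 1, the unadjusted D6 - b·D0 lies between D6 and D6 - D0, so in the same participants it is already bracketed. Arm-specific descriptive statistics are planned at both times. The bracket is only partial: those tests carry no covariates and no clustering, and baseline tests may include people without follow-up.

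On comparability, KPNC controls are matched and supply most participants, and OHSU controls are pods within the same clinics. This reduces concern about imbalance without removing it. The KPNC matching variables are not stated, and no matching is described for Legacy.

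On the binary outcomes, the reply is that 6-month status is the natural reading, so this is a wording slip in exploratory, unpowered analyses. That limits its weight. It does not supply the missing baseline ED covariate. The covariate list is open-ended, but a covariate that may be added later is not prespecified.

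Whether unmet needs means any or each type, and whether survey or record data define ED use, are missing details and not contradictions. The prior disparities survey reported unmet needs by type, and comparing the two utilisation sources is deliberate.

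**Conclusion.** The concern holds in two limited parts.

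1. **Binary outcomes:** the analysis as written cannot be fitted, and the natural repair leaves ED use without adjustment for its own baseline. This is minor, since the outcomes are exploratory and unpowered, but the results are meant to inform the choice of outcomes for the later trial.
2. **Primary outcomes:** a prespecified baseline-adjusted sensitivity model is missing. The planned primary analysis stands.

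The benefit of the second part is uncertain. For communication it is a confidence interval about 4-13% narrower, and power of about 84-90% instead of 80% if 0.4 is in SD of change. That rests on one-month data from 43 people, a paired t-test, equal SDs, no clustering, no other covariates and 100 per arm. Quoting a gain of 7-8% would be too precise, because it reflects only rounding of the pilot figures. The planned covariates could absorb some of the gain. For barriers there is no document-based estimate, and any disagreement between the models depends on a baseline gap that the documents do not give.

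**What to change.** **Binary outcomes.** State that unmet needs and ED use are analysed as status at 6 months, by logistic regression on study arm, adjusted for baseline status of the same variable and the covariates already listed. While that sentence is being rewritten, the coding of unmet needs and the source for ED use could be added in a clause; this is optional detail.

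**Communication and barriers.** Keep raw change as the stated primary analysis. Add one prespecified sensitivity model for each: the 6-month score regressed on study arm, its own baseline score and the planned covariates, within the same mixed-effects framework. Report it beside the primary result, together with the baseline difference between arms and its confidence interval.

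**Cost.** SAP wording and a small amount of extra analysis; the surveys are already given at both time points. The downside is that the two models may disagree, because they rest on different assumptions in a non-randomised design. Stating beforehand that change remains primary prevents a choice between them after the results are seen.
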